6.6 Questionnaires/Data Forms

6.6.1 Baseline medical history form

The baseline medical history form will ascertain general demographics, medical evaluation (for eligibility), degree of dyspnea at rest and related to daily activity, and other general respiratory symptoms. This will be completed by the research staff using a combination of adjudicating the electronic health record and direct enquiry from the participant or guardian.

6.6.2 Questionnaire during exercise: Modified Borg dyspnea scale

Ten-unit scale used to denote degree of dyspnea with exercise^{28,29} will be assessed at the 1-, 2- and 3-minute marks during the 3-minute step test, and again at post-1, post-2 and post-3.

Patient Instructions for Borg Dyspnea Scale

“This is a scale that asks you to rate the difficulty of your breathing. It starts at number 0 where your breathing is causing you no difficulty at all and progresses through to number 10 where your breathing difficulty is maximal. How much difficulty is your breathing causing you right now?”

6.6.3

0	Nothing at all
0.5	Very, very slight (just noticeable)
1	Very Slight
2	Slight
3	Moderate
4	Somewhat severe
5	Severe
6	
7	Very Severe
8	
9	Very, very severe (almost maximal)
10	Maximal

[figure not shown]
Questionnaire during Exercise: Dalhousie rating with exercise

This will be assessed at the 1-, 2- and 3-minute marks during the 3-minute step test.

The purpose of this test is to assess breathing and leg and body fatigue during exercise. Participants will be told that there is no right or wrong answer. The pictures in the Dalhousie questionnaire³⁰ will be shown to the

participant and asked to rate their experience from no difficulty at all, to the most difficulty you can imagine. (**Figure 4**)

Research staff will say, “You might feel this difficulty breathing in your chest or in your throat. Another scale simply asks you to tell us how hard it is to breathe—from nothing at all, to the hardest breathing imaginable. With the final set of pictures, tell us how your legs feel—from nothing at all, to the hardest imaginable.”

6.6.4 Retrospective questionnaire assessing dyspnea during daily activity: Baseline Dyspnea Index (BDI).

The BDI³¹ is a retrospective questionnaire assessing perceived dyspnea during activities of daily living 'on a typical day' over the past two weeks and will be assessed at Visits 2 and 3.

Baseline Dyspnea Index Questionnaire

I. Functional impairment

 Grade 4	No impairment	Able to carry out usual activities and occupation without shortness of breath.
 Grade 3	Slight Impairment	Distinct impairment in at least one activity but no activities completely abandoned. Reduction, in activity at work or in usual activities, that seems slight or not clearly caused by shortness of breath.
 Grade 2	Moderate Impairment	Patient has changed jobs and/or has abandoned at least one usual activity due to shortness of breath.
 Grade 1	Severe Impairment.	Patient unable to work or has given up most or all usual activities due to shortness of breath.
 Grade 0	Very Severe Impairment.	Unable to work and has given up most or all usual activities due to shortness of breath.
 W	Amount Uncertain	Patient is impaired due to shortness of breath, but amount cannot be specified. Details are not sufficient to allow impairment to be categorized.
 X	Unknown	Information unavailable regarding impairment.
 Y	Impaired for Reasons Other than Shortness of Breath.	For example, musculoskeletal problem or chest pain. Usual activities refer to requirements of daily living, maintenance or upkeep of residence, yard work, gardening, shopping, etc.

II. Magnitude of Task

 Grade 4	Extraordinary	Becomes short of breath only with extraordinary activity such as carrying very heavy loads on the level, lighter loads uphill, or running. No shortness of breath with ordinary tasks.
 Grade 3	Major	Becomes short of breath only with such major activities as walking up a steep hill, climbing more than three flights of stairs, or carrying a moderate load on the level.
 Grade 2	Moderate	Becomes short of breath with moderate or average tasks such as walking up a gradual hill, climbing fewer than three flights of stairs, or carrying a light load on the level.
 Grade 1	Light	Becomes short of breath with light activities such as walking on the level, washing, or standing.
 Grade 0	No Task	Becomes short of breath at rest, while sitting, or lying down.
 W	Amount Uncertain	Patient's ability to perform tasks is impaired due to shortness of breath, but amount cannot be specified. Details are not sufficient to allow impairment to be categorized.
 X	Unknown	Information unavailable regarding limitation of magnitude of task.
 Y	Impaired for Reasons Other than Shortness of Breath.	For example, musculoskeletal problem or chest pain.

III. Magnitude of Effort

 Grade 4	Extraordinary	Becomes short of breath only with the greatest imaginable effort. No shortness of breath with ordinary effort.
 Grade 3	Major	Becomes short of breath with effort distinctly submaximal, but of major proportion. Tasks performed without pause unless the task requires extraordinary effort that may be performed with pauses.
 Grade 2	Moderate	Becomes short of breath with moderate effort. tasks performed with occasional pauses and requiring longer to complete than the average person
 Grade 1	Light	Becomes short of breath with little effort tasks performed with little effort or more difficult tasks performed with frequent pauses and requiring 50-100% longer to complete than the average person might require.
 Grade 0	No effort	Becomes short of breath at rest, while sitting, or lying down.
 W	Amount Uncertain	Patient's exertional ability is impaired due to shortness of breath, but amount cannot be specified. Details are not sufficient to allow impairment to be categorized.
 X	Unknown	Information unavailable regarding limitation of effort.
 Y	Impaired for Reasons Other than Shortness of Breath.	For example, musculoskeletal problems or chest pain.

6.6.5 Retrospective questionnaire assessing dyspnea during daily activity: MRC Breathlessness scale.

The MRC breathlessness questionnaire is a retrospective questionnaire assessing perceived dyspnea during activities of daily living 'on a typical day' over the past two weeks and will be assessed at Visits 2 and 3. The score ranges from 0 to 5 with higher score representing worse dyspnea.^{31,32}

The MRC Breathlessness scale	
Grade	Degree of breathlessness related to activities
0	No breathlessness even with strenuous exercise
1	Not troubled by breathlessness except on strenuous exercise
2	Short of breath when hurrying on the level or walking up a slight hill
3	Walks slower than most people on the level, stops after a mile or so, or stops after 15 minutes walking at own pace
4	Stops for breath after walking about 100 yards or after a few minutes on level ground
5	Too breathless to leave the house, or breathless when undressing

6.7 Stair-step Challenge.

The Stair-step Test is a recognized clinical procedure used to measure cardiovascular fitness in adults aged 18 and up. The Bench Stepping Test has been adapted for children aged 5-18 for the purposes of this study. It has been validated in other clinical studies designed to measure the effectiveness of exercise and/or dietary interventions to improve cardiovascular fitness and other clinical measures related to obesity.^{33,34}

6.7.1 Preparation for administration of Stair-step Test

1. Ensure that all of the necessary materials are present. Study materials include a stable step, 8 risers, metronome, timer, pulse oximeter, and chair.
2. Step Setup
 - a. For ages 8-9: Have child set one foot on the floor and one foot on the step and measure with protractor. Protractor should read between 20 and 30 degrees. Add/remove risers as necessary.
 - b. For ages 10-17: Set step on two risers (8 inches).
 - c. If patient is $\geq 6'0"$, have them place one foot on the floor and one on the riser and measure with protractor. Add/remove a riser until protractor reads between 20 and 30 degrees.
 - d. Patients over 300 lbs. do not complete the step test
3. Set metronome to beat at 96 beats per minute.
4. Set timer for 3 minutes.
5. Train the subject to complete the Step Test.
 - a. In time with the metronome, the subject will step one foot onto the step (1st beat), step the second foot up (2nd step), step down with one foot (3rd beat), and step down with other foot (4th beat).
 - b. Allow a short rest before beginning test.

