6.2.2 Visit 2 (Day 0)

General Visit Description: Visit 2 will be Day 0, will re-confirm eligibility prior to randomization, will include randomization if eligible and will start the intervention and observation period. Participants must not newly meet any exclusion criteria and must continue to meet all inclusion criteria. Inclusion criteria for randomization will include collection of at least 7 days of valid actigraphy data (confirmed at Visit 2).

Equipment/Supplies needed: Activity tracker (from participant), accompanying smart device(s), printed questionnaires, participant informational handouts, PrO2 trainer, Stair Step Test equipment.

Anticipated duration: 60 minutes.

Visit 2 Procedures:

1. Assessment of baseline actigraphy (participants must have worn the Vivosmart 4 activity tracker for at least 7 full days (max of 14) prior to randomization. If not,

the date of Visit 2 may be extended for an additional 4-14 days for a continuation Visit 2).

2. Questionnaires and eligibility assessment (eligibility checklist, questionnaires can be printed or electronic) (see questionnaires section).
3. Interval history and event monitoring.
4. Measure Maximal inspiratory pressure (MIP) before and after step test (see MIP section).
5. Stair Step Test (see stair step section).
6. Retrospective dyspnea scoring that assesses dyspnea from daily activities (Baseline Dyspnea Index (BDI), the MRC Breathlessness scale), and during the step-test (Modified Borg Dyspnea scale and Dalhousie Dyspnea/Perceived Exertion Scale).
7. Randomization (see the randomization procedure section).
8. Study instruction refresher and questions/answers.
9. PrO2 Fit app and device IMR training.
10. Refresher Training (question and answers) on the use of Vivosmart 4 activity tracker.
11. Discuss plan for phone call visits and future study visit. Plan next phone call check-in visit (Day 7).

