6.2.3 Visit 3 (Day 42) Final In-person visit

General Visit Description: Visit 3 will be on approximately day 42, final assessment of the study. This visit is preferred as an in-person study visit, but may be conducted as an in-home visit if needed (as with Visit 2). Day 42 (+/- 5 days) will be the goal day for study Visit 3. With PI approval, Visit 3 may be conducted up to 14 days away from Day 42, if necessary.

Equipment/Supplies needed: Scale, stadiometer, activity tracker (from participant), accompanying smart device(s), printed questionnaires (or tablet-based REDCap questionnaires), PrO2 trainer (from participant), Stair Step Test equipment, assignment and thank you letter.

Anticipated duration: 60 minutes.

Visit 3 Procedures:

1. Reassessment of participant height, weight, and BMI.
2. Dyspnea scoring assessing daily activities [Baseline Dyspnea Index (BDI), the MRC Breathlessness scale].
3. Dyspnea scoring during the step-test (Modified Borg Dyspnea scale and Dalhousie Dyspnea and Perceived Exertion Scale).
4. Adverse effect monitoring.
5. Measure Maximal inspiratory pressure (MIP) before and after step test.
6. Stair Step Test.
7. Follow up actigraphy (participants must have worn the Vivosmart 4 activity tracker for at least 7 full days (max of 10) during week prior to Visit 3).
8. Patient satisfaction questionnaire.
9. Close out procedures:
 - i. Assignment envelope;
 - ii. Close out letter (i.e. thank you letter).

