6.7.2 Administering the Step Test

- Measure baseline (at time 0) heart rate with pulse-oximetry before child begins step test.
- Have child step up and down step at 96 bpm for 3 minutes.
- Assess dyspnea scores at minutes 1, 2 and 3, and post-1, post-2 and post-3.

- After 3 minutes, end the stepping and check child's heart rate on pulse-oximetry (post-1).
- Direct child to sit in chair for one minute, then check heart rate again (post-2).
- Direct child to remain in chair for another minute, then check heart rate (post-3).

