6.7.3 Recording heart rate and pulse oximetry

- a. Heart rate at baseline, post-1, post-2 and post-3.
- b. Pulse oximetry at baseline, post-1, post-2 and post-3.

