10. STATISTICAL CONSIDERATIONS

10.1 Study Hypotheses

Primary Specific Aims: Compare measures of satisfaction, adherence and safety between patients randomized to IMR as compared to sham to demonstrate IMR as an acceptable add-on intervention that promotes greater activity in children with obesity with no safety concerns. More satisfaction and adherence are expected in the IMR group compared to sham.

- Hypothesis 1: More than 80% of participants will be satisfied with active IMR at study completion.
- Hypothesis 2: Total active IMR adherence will be >80% of planned IMR repetitions.
- Hypothesis 3: Active IMR will not be associated with any serious adverse reactions.

Secondary Aim: Compare inspiratory strength (measured by mean change in MIP) in IMR versus sham participants to demonstrate changes in inspiratory muscle functioning and dyspnea following IMR. Also, to demonstrate changes in daily physical activity following IMR versus sham participants.

- Hypothesis 1: IMR will significantly increase inspiratory strength (measured by mean change in MIP) with more improvements in IMR compared to participants receiving sham.
- Hypothesis 2: IMR will reduce patient-reported dyspnea scores from activities of daily living and during the step test.
- Hypothesis 3: IMR will lead to reduced sedentary time, increased moderate-strenuous time and increased total daily activity measured by a wrist-worn continuous activity tracking monitor.

Exploratory Aim: Demonstrate changes in exercise capacity following IMR versus sham participants.

- Hypothesis 1: IMR will reduce the peak heart rate increase induced by the step test in IMR compared to sham participants.

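### The Visit 2 step height need not be recorded or reused at Visit 3, so some children may be retested at a different workload

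*Combined protocol and SAP*

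**What the plan says.** Section 6.7.1 gives one set-up rule with three branches:

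- Ages 8-9: one foot on the floor, one on the step, then "Protractor should read between 20 and 30 degrees. Add/remove risers as necessary".
- Ages 10-17: "For ages 10-17: Set step on two risers (8 inches".
- Height 6 feet or more: "Add/remove a riser until protractor reads between 20 and 30 degrees".

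Table 4 and the Visit 2 and Visit 3 procedures schedule the test at both visits. Cadence and duration are fixed in Section 6.7.2: "Have child step up and down step at 96 bpm for 3 minutes". Section 6.7.3 asks for "Heart rate at baseline, post-1, post-2 and post-3" and for oximetry at the same times. Riser count and step height are not on the list.

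Section 10.1 states the exploratory hypothesis: "IMR will reduce the peak heart rate increase induced by the step test in IMR compared to sham participants". Secondary Hypothesis 2 in the same section also names dyspnea during the step test, although the endpoint list in Section 10.2 names only dyspnea in daily activities. Section 6.5 measures MIP before and after the step test. The ANCOVA in Section 10.10 adjusts for the baseline value of the outcome; step height is not in the model.

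**The concern.** A change score from a fixed-workload test is interpretable only if the workload is the same both times. With cadence and duration fixed, step height sets the vertical work per kilogram. The rule depends on current age and on an angle range, and no section carries the Visit 2 height forward. Under the text as written, three kinds of child could be tested at two heights:

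- a child set by angle at both visits, if more than one riser setting falls within the band;
- a child who turns 10 between visits and moves to the fixed step;
- a child who reaches 6 feet between visits and moves to the angle rule.

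Because the setting is not among the recorded items, the analyst could neither see a change nor adjust for it. At stake is the precision of the step-test heart-rate change, step-test dyspnea and MIP after the test, in a trial of 15 per arm.

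**Working it through.** **1. The plan's own figure.** Table 5 gives power 0.509, 0.793 and 0.910 at N=30 for d = 0.75, 1.05 and 1.25. Inputs: n = 15 per arm, two-sided alpha 0.05 (Section 10.7). A two-sample t-test has df = 2n - 2 = 28 and noncentrality d × √(n/2); for d = 0.75 this is 0.75 × √7.5 = 2.05. The noncentral t distribution returns the same three values, and all 24 cells of the table reproduce within 0.0005. The table is not in dispute; it is the reference for step 6.

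**2. Width of the angle band.** The landmarks for the protractor are not defined, so two geometries were tried, with L a length fixed by the child's build and stance:

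- h = L sin θ: highest/lowest = sin 30° / sin 20° = 0.500 / 0.342 = 1.46
- h = L tan θ: highest/lowest = tan 30° / tan 20° = 0.577 / 0.364 = 1.59

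The band is a range of heights, not one height.

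**3. Can two riser settings both comply?** Riser thickness is not given, so it is an assumption. Take every L for which 8 inches complies, and ask for what share 8 inches plus or minus one riser also complies.

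| Riser (assumed) | Sine | Tangent |
|---|---|---|
| 2 inches | 67% | 90% |
| 4 inches | 0% | 15% |

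With 2-inch risers a second compliant setting is common. With 4-inch risers it is rare or impossible.

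**4. Workload.** 96 beats/min ÷ 4 beats per cycle × 3 min = 72 cycles. Vertical climb at 8 inches is 72 × 8 × 0.0254 = 14.6 m. At 6 inches it is 72 × 6 × 0.0254 = 11.0 m, a 25% reduction. The documents do not say how heart rate or dyspnea would respond.

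**5. How many children?** Assume ages uniform over the ten years 8-17.

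- Aged 8-9: 30 × 2/10 = 6. This counts children under the angle rule, not children whose height changes.
- Turning 10 between visits: 30 × 1/10 × 42/365.25 = 0.34. At the latest Visit 3 (day 56), 30 × 1/10 × 56/365.25 = 0.46.
- 6 feet or taller: not given.

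**6. Effect on precision.** Let a share q of children have a shift of k SD with random sign. The variance of the change becomes 1 + qk², and the effective d is d/√(1 + qk²). Both q and k are assumptions.

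| q, k | Variance factor | Power at d = 0.75 / 1.05 / 1.25 |
|---|---|---|
| none | 1 | 0.509 / 0.793 / 0.910 |
| 10%, 0.5 | 1.025 | 0.500 / 0.783 / 0.904 |
| 20%, 1 | 1.2 | 0.441 / 0.717 / 0.855 |

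The last row is severe: q = 20% means a changed height for as many children as the whole 8-9 age group in step 5.

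**7. Chance imbalance.** If one arm has m more children than the other with a same-direction shift of k SD, the between-arm difference moves by mk/15. For m = 1 to 3 and k = 0.5 to 1.5, this runs from 1 × 0.5/15 = 0.03 SD to 3 × 1.5/15 = 0.30 SD.

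**The case against.** Several stronger readings are tempting, and the documents do not support them.

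- *A reader might infer that the step is set afresh at each visit.* The text does not say so; it is silent on whether the earlier height is kept. Section 12.7 also refers to a manual of procedures and forms instructions, which may cover the point. What stands is that the protocol does not require the same height.
- *A reader might infer that any child is exposed.* Children aged 10-17 under 6 feet have the 8-inch step at both visits and are probably most of the sample. Limb length hardly changes in six weeks, so the angle rule will often return the same setting. For tall adolescents, adding or removing a riser until the angle fits works as a stopping rule and may be largely repeatable.
- *A reader might infer confounding by arm.* Allocation is randomized 1:1 (Section 5.4.1), and staff who assess outcomes are blinded (Section 4.2). A height change should be unrelated to arm.
- *A reader might infer a workload change of up to 50%.* That needs 4-inch risers. Going from 8 to 4 inches is a ratio of 2.0, which the band excludes. Going from 8 to 12 is 1.5, excluded under the sine geometry and only marginal under the tangent. For a child who turns 10 the band sets no limit, but fewer than one such child is expected.
- *The endpoints are minor.* This is largely true. Heart rate is exploratory. Step-test dyspnea is in a hypothesis but not in Section 10.2. Table 1 and Section 10.2 list change in MIP without naming a post-exercise value.

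These points limit the size of the problem but do not close the gap. The rule as written permits different workloads at the two visits, and the listed data would not reveal it.

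**Conclusion.** The point holds as a low-severity gap in standardization. For children aged 8-9, those 6 feet or taller, and the few who change category between visits, Section 6.7.1 allows a different step height at Visit 3, and nothing in the protocol records it. A 2-inch change from 8 inches would alter vertical work by 25%.

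The consequence is added within-child noise and possible chance imbalance. Under the assumptions shown, power at d = 0.75 falls from 0.509 to between 0.500 and 0.441. A within-arm mean change would be biased only if heights shifted systematically in one direction. The primary acceptability endpoints are untouched.

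The figures rest on assumed angle geometry, riser size, age mix, share of children affected and size of shift. The absence of a requirement to record or reuse the height rests on the text alone.

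**What to change.** Add to Section 6.7.1, with a matching field on the data form: *Record the number of risers (step height) used at Visit 2 and use the same setting at Visit 3; if it cannot be used, record the setting used and the reason.* Logged departures would also allow a sensitivity analysis without those children.

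The cost is one sentence and one data field. No endpoint, sample size or analysis model changes. One downside should be accepted openly: for the few children whose age or stature category changes, the Visit 3 height may fall outside the age or angle rule. The staff's safety judgment still applies, which is why the wording allows a recorded exception.

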6.7.2 Administering the Step Test

- Measure baseline (at time 0) heart rate with pulse-oximetry before child begins step test.
- Have child step up and down step at 96 bpm for 3 minutes.
- Assess dyspnea scores at minutes 1, 2 and 3, and post-1, post-2 and post-3.

- After 3 minutes, end the stepping and check child's heart rate on pulse-oximetry (post-1).
- Direct child to sit in chair for one minute, then check heart rate again (post-2).
- Direct child to remain in chair for another minute, then check heart rate (post-3).

6.7.3 Recording heart rate and pulse oximetry

- a. Heart rate at baseline, post-1, post-2 and post-3.
- b. Pulse oximetry at baseline, post-1, post-2 and post-3.

6.11 Specimen Preparation, Handling, Storage and Shipping

No biological specimens will be collected.

7. STUDY PRODUCT DESCRIPTION

7.1 Dosage and Study Intervention Information

7.1.1 Dose of inspiratory muscle training

Arm A: The **intervention group** will be required to achieve a pressure target that is **75% of their MIP** for each repetition. Participants will perform 3 sets of 50 inspiratory breaths 3 times per week.

Arm B: The **sham group** will be required to achieve a pressure target that is **15% of their MIP** for each repetition. Participants will perform 3 sets of 50 inspiratory breaths 3 times per week.

